Since this study is expressly recruiting Subjects with irritability, which may coexist with anger, aggression, depression and suicidality, these symptoms represent expected adverse events due to the presence of HD, which will sometimes warrant intervention. Physicians who take care of HD and other movement disorder patients will have encountered these symptoms and will already be well versed in their management and in assessing the need for further assessment and intervention. Any Investigator who has completed a movement disorders fellowship will have had extensive training in management of suicidal ideation, worsening agitation and irritability, and other psychiatric symptoms in HD and other movement disorders. Training in the assessment and management of behavioral symptoms is provided to all HSG investigators at yearly HSG meetings as part of the Educational Program and will be included in the Investigator and Coordinator meetings. The site Investigator will be required to make a documented determination about whether clinical referral to a treating physician or acute intervention like hospitalization is warranted for AE s in this category that are grade 2 and above.

Investigators will be asked to characterize aggression AEs as:

- 1) Verbal aggression
- 2) Physical aggression: if physical: a) aggression toward self (self-injury, suicidal behavior); b) aggression toward others; c) aggression toward property; or d) aggression toward pets

Investigators will also be asked to report the outcome of these AEs:

- 1) Mental Health Referral
- 2) Emergency Room Visit
- 3) Psychiatric Hospitalization
- 4) Concomitant medications added

As part of the site initiation visit, sites will be given a worksheet to complete to document their local procedures for:

- 1) Escorting a patient from a study visit to the Emergency Room if needed due to exacerbation of behavioral symptoms
- 2) Setting up a rapid mental health referral (including names and contact for local psychiatrists, psychologists)
- 3) Facilitating a psychiatric hospitalization (contact names and numbers for local units with which they have a relationship)
- 4) Dealing with emergency phone call from Subject or care partner for worsening of behavioral symptoms

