The above equation indicates that a power analysis for planned sample size requires candidate values for π_P , π_T and δ , for fixed type 1 error rate (α) and type 2 error rate (β). Following the practice of the Huntington Study Group (HSG 1998; 2003; 2004; 2009), the margin was set at $\delta = 0.50$ for all analyses, though a follow-up margin sensitivity analysis was performed (see below). A difference of 50% between P and T is considered acceptable because of the paucity of effective treatments for HD (HSG 1998). For the remaining parameters, plausible values were based on published literature for randomized clinical trials (RCTs) in HD.

Table 4 below shows completer information for P and T groups of six HD RCTs employing various drugs.

Table 4. Tolerability information from HD clinical trials.

Study	Drug	N	Completer Percentage		
			Placebo	Treatment	Difference
HSG (2009)	Tetrabenazine	84	97%	91%	6%
Kieburtz (2010)	Latrepirdine	91	82%	87%	5%
HSG (1998)	OPC-14117	64	94%	81% ^a	13%
HSG (2003)	Riluzole	63	91%	87% ^a	4%
HSG (2004)	Minocycline	60	96%	78% ^a	18%
Squitieri (2013)	Pridopidine	353	86%	86% ^a	0%

[figure not shown]
Note. ^aPercentage is the minimum among multiple treatment arms.

Placebo completion rate ranged from 82%-97% and the group difference ranged from 0%-18%. In light of the information in Table 4, sample size was computed for

$\pi_P = 0.80, 0.85, 0.90, 0.95$ and $\pi_P - \pi_T = 0.01, 0.02, \dots, 0.19, 0.20$. It should be noted that the minimum $\pi_P = 0.80$ is less than any placebo value in Table 4, and the maximum $\pi_P - \pi_T = 0.20$ is greater than any difference in Table 4, so these values constitute reasonable bounds for selecting required sample size. The non-inferiority test is single-tailed, and the type I error rates of $\alpha = .05 / 2 = .025$, and $\alpha = .10 / 2 = .05$ were used to allow for two comparisons (each dose level versus placebo), with power set at 80% ($\beta = 0.20$).

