An additional consideration is that using the asymptotic test with our estimated sample size might not be optimal. The asymptotic test can be inaccurate with smaller sample sizes, especially when π_P (or π_T) is close to 1, as is anticipated in the proposed study (cf Table 4) (Fagerland 2011). Computer-intensive exact methods can have better performance under these conditions (Santner 2007). The exact method discussed by Wang (2010) will be used for the proposed analysis of tolerability and safety (the latter is discussed below). Wang's method appears to have superior performance to other approaches, and software is readily available (Wang 2013).

Secondary Aim: Safety. The secondary aim of the analysis is safety, with the endpoint defined as the proportion of participants who experience an adverse event (AE). A non-inferiority analysis for safety will be performed, similar to that discussed for tolerability. Primary focus will be on the comparison of 160mg vs placebo. H_0 for non-inferiority will be evaluated using the methods previously described with the same margin of difference, $\delta = 0.50$.

Consistent with the recent JAMA Guide to Statistics and Medicine (Detry 2014) the analysis will be performed consistent with the intent-to-treat principle, meaning an attempt will be made to analyze all enrolled patients. Missing data methods, such as imputation, might be used to handle dropout (note this is not an issue for the tolerability analysis as the proportion of completers is the endpoint).

Exploratory Aim: Activity of Measures. The exploratory aim is to examine several measures of irritability and other problem behaviors and clinical assessment for activity signal. Measures will be compared to each other and also compared to clinical assessments in order to examine relative

effect sizes. The endpoint will be rate of change (slope) over 12 weeks. Linear mixed models (LMMs) (Verbeke 2000) will be used to examine slope differences among the placebo and treatment groups. LMMs are appropriate for the analysis because they account for dependency due to repeated measures and can be estimated with maximum likelihood (ML) procedures.

Consistent with the intent-to-treat principle, ML estimation can accommodate missing data under the assumption that the missing data mechanism is ignorable (Little 1987).

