$$H_0: \pi_{\text{placebo}} - \pi_{120\text{mg}} \geq \delta$$

vs.

$$H_A: \pi_{\text{placebo}} - \pi_{120\text{mg}} < \delta.$$

For the purposes of this study, the non-inferiority margin was set to $\delta = 0.5$, which is the same value used in a series of clinical trials sponsored by the Huntington Study Group ([HSG, 1998](#); [HSG, 2003](#); [HSG, 2004](#); [HSG/TETRA-HD Investigators, 2009](#)). Using this threshold means that when H_0 is rejected, $\pi_{120\text{mg}} - \pi_{\text{placebo}} < 0.5$. Or, equivalently, the tolerability in the treated group is less than 50% lower than the tolerability in the placebo group, which is taken to be a negligible (non-meaningful) difference in tolerability. Thus, non-inferiority of tolerability within the margin is consistent with the rejection of the null hypothesis and will constitute a Go decision for further consideration of that dose of SRX246, perhaps in a phase IIb study to detect signs of activity. Conversely, failure to reject the null hypothesis would imply that there could be tolerability concerns and will result in a No-Go decision for that dose. Note that rejection of H_0 does not necessarily mean there is strict equivalence among the groups (i.e., does not imply that the difference is 0). Rather, any tolerability difference is below the acceptable 50% threshold.

The statistical test of H_0 will be performed using a one-sided CI for the difference of the proportions based on exact methods. Exact methods have known sampling distributions in contrast to asymptotic methods that have approximate sampling distributions ([Agresti, 2003](#)). Exact methods are preferable because their confidence intervals (CIs) have a minimum coverage probability, especially for small sample sizes (the minimum is $1 - \alpha$). The CI to be used corresponds to inverting a family of exact tests, with the 97.5% CI ($\alpha = 0.025$) including all the values that are not rejected at the .025 level in the corresponding test. Though an exact CI has a minimum coverage probability of $1 - \alpha$, its length can be too long, which means the associated inverted test has low statistical power. To address this issue, and to ensure that H_0 is evaluated using the highest possible statistical power, a computer-intensive method will be used to select the shortest one-sided CI for testing ([Wang, 2010](#)).

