8. SECONDARY ANALYSIS

Secondary Objective: *The secondary objective is to evaluate the safety of SRX246.*

The safety objective will be met by conducting a non-inferiority test of the proportion of study participants with AEs or SAEs among the placebo group and each of the treatment groups (separate tests for placebo vs 120 mg and placebo vs 160 mg). The safety analysis will be conducted in a similar manner as the tolerability analysis. Each study participant will be classified as having experienced a treatment-emergent AE or SAE (event = "Yes") or not (event = "No"). Suppose the proportion of events in the placebo group is now denoted as π_{placebo} and the proportion of events in the 120 mg group is now $\pi_{120\text{mg}}$, with $\theta = \pi_{\text{placebo}} - \pi_{120\text{mg}}$. The same onesided CI will be used to test the same null hypothesis ($H_0: \theta \geq \delta$) with the same threshold ($\delta = 0.5$) as in the tolerability analysis. Each treatment group (120 mg, 160 mg) will be compared to the placebo group using $\alpha = 0.025$, meaning a $1 - \alpha = 0.975$ one-sided CI will be used for each test. Results will be summarized as shown in Table 3 below.

Table 3. Summary of Safety Analyses

	Placebo (N = XX)	120 mg (N = XX)	160 mg (N = XX)
Any AE	XX (XX%)	XX (XX%)	XX (XX%)
Any Treatment-Related AE	XX (XX%)	XX (XX%)	XX (XX%)
Any Serious AE	XX (XX%)	XX (XX%)	XX (XX%)
Early Drug Withdrawals (Any)	XX (XX%)	XX (XX%)	XX (XX%)
Early Drug Withdrawals (Due to AE)	XX (XX%)	XX (XX%)	XX (XX%)
Early Terminations (Any)	XX (XX%)	XX (XX%)	XX (XX%)
Early Terminations (Due to AE)	XX (XX%)	XX (XX%)	XX (XX%)
Deaths (Any)	XX (XX%)	XX (XX%)	XX (XX%)
Deaths (Due to AE)	XX (XX%)	XX (XX%)	XX (XX%)

In addition to an overall comparison, this hypothesis will be repeated for assessing the percentage of study participants having at least one treatment-emergent AE within each MedDRA system organ class (SOC). If there are specific differences within any specific SOC, then additional tests will compare differences across groups for specific MedDRA preferred terms in order to further explore the cause of the observed differences. Finally, the subset of treatment-related SAEs will be analyzed in the same manner described above.

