The above equation indicates that a power analysis for this scenario requires estimates for the values of $\pi_{placebo}$, π_{120mg} , and δ . A power analysis was conducted using estimated values of the parameters obtained from previous research. Following the practice of the Huntington Study Group ([HSG, 1998](#); [HSG, 2003](#); [HSG, 2004](#); [HSG/TETRA-HD Investigators, 2009](#)), the margin was set at $\delta = 0.50$ for all analysis. A difference of <50% between groups is considered acceptable because of the paucity of effective treatments for HD ([HSG, 1998](#)). For the remaining parameters, plausible values were based on published literature for relevant randomized clinical trials (RCTs) in HD ([HSG, 1998](#); [HSG, 2003](#); [HSG, 2004](#); [HSG/TETRA-HD Investigators, 2009](#); [Kieburtz et al, 2010](#); [Squitieri et al, 2013](#)). [Table 4](#) below shows completer information for placebo and treatment groups of six HD RCTs employing various drugs (for studies with multiple treatment groups, group with the smallest percentage of completers is shown). Placebo completion rates across the six studies ranged from 82%-97%, and the observed treatment group differences ranged from 0%-18%.

In light of the information in Table 4, sample size was computed for:

- $\pi_{placebo} = 0.80, 0.85, 0.90, 0.95$, and
- $\pi_{placebo} - \pi_{treatment} = 0.01, 0.02, \dots, 0.19, 0.20$.

[figure not shown]
It should be noted that the minimum $\pi_{placebo} = 0.80$ is less than any placebo value in Table 4, and the maximum difference ($\pi_{placebo} - \pi_{120mg}$) of .20 is greater than any observed difference in Table 4. Therefore, these values constitute reasonable bounds for assessing required sample size for this study. The non-inferiority test is single-tailed, and type I error rates of $\alpha = 0.05/2 = 0.025$ and $\alpha = 0.10/2 = 0.05$ were used to allow for two comparisons (each dose level versus placebo), with target power set at 80%.

Table 4. Tolerability Statistics from HD Clinical Trials.

Study	Drug	N	Placebo	Treatment	Difference
HSG (1998)	OPC-14117	64	94%	81%	13%
HSG (2003)	Riluzole	63	91%	87%	4%
HSG (2004)	Minocycline	60	96%	78%	18%
HSG/TETRA-HD (2009)	Tetrabenazine	84	97%	91%	+6%
Kieburtz et al (2010)	Latrepirdine	91	82%	87%	-5%
Squitieri et al (2013)	Pridopidine	353	86%	86%	0%

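### The 0.50 margin set for completion is reused for adverse events without a safety reason, so an observed excess of 28 to 31 points on drug can be declared non-inferior

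*SAP*

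**What the plan says.** SAP section 8 meets the safety objective by a non-inferiority test on the proportion of participants with any treatment-emergent AE or SAE, each dose against placebo. It uses the same one-sided 97.5% interval and the same threshold of 0.5 as tolerability. The test is then extended twice:

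- By organ class: "this hypothesis will be repeated for assessing the percentage of study participants having at least one treatment-emergent AE within each MedDRA system organ class".
- To related serious events: "Finally, the subset of treatment-related SAEs will be analyzed in the same manner described above".

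A further step depends on the organ-class results: "If there are specific differences within any specific SOC, then additional tests will compare differences across groups for specific MedDRA preferred terms". What counts as a specific difference is not defined.

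Protocol 8.2, under the secondary aim, has the same carry-over: "H_0 for non-inferiority will be evaluated using the methods previously described with the same margin of difference".

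The reasons for 0.50 are earlier Huntington Study Group practice and the lack of effective treatments. Protocol 8.2 says "A difference of 50% between P and T is considered acceptable because of the paucity of effective treatments for HD" and SAP section 9 says "A difference of <50% between groups is considered acceptable because of the paucity of effective treatments for HD", both in the sample-size argument for completers. SAP section 7 describes the threshold in terms of tolerability only: "Rather, any tolerability difference is below the acceptable 50% threshold".

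**The concern.** A margin states how much worse the drug may be before it matters. Accepting up to 50 points fewer completers is one judgement; accepting up to 50 points more participants with an adverse event, or with a treatment-related SAE, is another. The documents make only the first.

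A margin this wide at this sample size makes the test insensitive. The report could state non-inferior safety for an excess whose ordinary confidence interval excludes zero. The risk is greatest in two places:

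- **Low background rates**, such as treatment-related SAEs, where the drug arm needs many events before the test fails.
- **High background rates**, such as any AE, where the ceiling of 100% leaves no room to fail. Some psychiatric organ-class terms may also belong here, since protocol section 7 says of behavioral symptoms that "these symptoms represent expected adverse events due to the presence of HD".

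**Working it through.** **Inputs.** 36 per arm (SAP section 9); one-sided alpha 0.025 per comparison and an exact interval (SAP section 7); margin 0.50 (SAP section 8). Neither document gives a background AE rate, so results are shown across placebo rates.

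**The plan's own figure.** Safety has no sample-size calculation of its own; 36 comes from completers at 0.80 versus 0.60. The standard formula gives

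n = (1.960 + 0.842)² × (0.80×0.20 + 0.60×0.40) / (0.50 − 0.20)² = 7.849 × 0.40 / 0.09 = 34.9, so 35 per arm.

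This matches the protocol's 35 and is close to the SAP's 36.

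**Direction.** SAP section 8 keeps placebo minus drug although an event is now the bad outcome. As written, 0/36 placebo versus 36/36 drug gives an upper limit of about −0.90 and passes. That is a separate error. Everything below assumes it is corrected: H0: p_drug − p_placebo ≥ 0.50, rejected if the exact upper 97.5% limit is below 0.50.

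**Cut-offs.** An exact unconditional test with score ordering, maximised over the unknown placebo rate, has attained size 0.0249. The SAP's smallest one-sided interval, coded independently, gives the same boundary.

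| Placebo events (of 36) | Largest drug count still passing | Excess |
|---|---|---|
| 0 | 11 | 11 (30.6 points) |
| 5 | 16 | 11 (30.6 points) |
| 6 | 16 | 10 (27.8 points) |
| 18 | 28 | 10 (27.8 points) |
| 24 | 35 | 11 (30.6 points) |
| 25 or more | 36 | no drug result can fail |

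The excess is 11 participants for 0–5 and 20–25 placebo events, and 10 for 6–19.

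- 0/36 vs 11/36: SAP-type upper limit 0.483, passes. Exact two-sided 95% CI about 16 to 48 points; Fisher p = 0.0004.
- 0/36 vs 12/36: upper limit 0.511, fails.
- 18/36 vs 28/36: upper limit 0.475, passes. Exact 95% CI about 5 to 48 points; Fisher p = 0.026.

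The Wald, Newcombe and Miettinen–Nurminen limits would also pass 0/36 vs 12/36.

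**Chance of passing.** Joint binomial probability of falling inside these cut-offs, minimum and maximum over all possible placebo rates:

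| True excess on drug | Chance declared non-inferior |
|---|---|
| 20 points | 79% to 96% |
| 25 points | 64% to 83% |
| 30 points | 47% to 61% |
| 35 points | 29% to 37% |
| 40 points | 16% to 19% |

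Examples: 0% vs 25%, 83%; 50% vs 80%, 49%; 60% vs 100%, 16%.

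**Ceiling.** If the true placebo any-AE rate is 70%, 75% or 80% (assumed), the chance of 25 or more placebo events, so that the test cannot fail, is 61%, 83% or 96%.

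**The case against.** The strongest case on the other side is about consequence. Go/No-Go depends on tolerability alone. Table 3 shows counts by arm and, unlike Table 2, has no decision row, so a reader would see 0% versus 31% directly. SAEs are reported within 24 hours and reviewed by the medical monitor, and the DSMB reviews safety as well. This stands, and it limits the point to the formal statement in the report. It does not remove it: SAP section 8 makes this test the means of meeting the safety objective, and Table 3 has no difference, no interval and no row for organ classes or treatment-related SAEs.

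Other objections stand in part:

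- **The figures assume the direction is corrected.** True, but correcting the direction alone leaves the margin problem in place.
- **0/36 vs 11/36 is the extreme case.** Fair. At 18/36 vs 28/36 the evidence of harm is weaker, though zero is still excluded at the trial's own one-sided 0.025.
- **36 per arm was the initial plan.** The analysed numbers may differ. At 30 per arm, spot checks give a largest passing excess of 23 to 30 points. The missing rationale does not depend on n.
- **The replacement flag is weak at low rates and depends on the method.** True. For 0% vs 10% it is raised 49% of the time with the score-ordered exact method and 15% with Fisher; for 2% vs 10%, 26% and 8%. The present test is no better there: with no placebo events it fails only at 12 or more of 36 on drug.

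**Conclusion.** The concern holds and should be fixed. The margin of 0.50 is applied to any AE or SAE, to each organ class and to treatment-related SAEs with no safety rationale in either document. With 36 analysed per arm, alpha 0.025 one-sided and the direction corrected, an observed excess of 28 to 31 points passes for up to 25 placebo events, and nothing can fail from 25 upward. The test is not empty, since a true 40-point excess fails more than 80% of the time, but it cannot support a statement that safety is non-inferior. The cut-offs rest on the exact method and on n = 36. The Go/No-Go decision is not affected.

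**What to change.** In SAP section 8:

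1. Draw no non-inferiority conclusion from a margin of 0.50 for organ-class AEs or treatment-related SAEs.
2. For these, and for any AE and any SAE, report for each dose the drug-minus-placebo risk difference with a two-sided exact 95% CI. Name the method (for example, inversion of the score-ordered unconditional test).
3. State that a lower limit above 0 is an unadjusted screening flag that triggers preferred-term review, and is not a test of safety. This supplies the undefined trigger.
4. If the overall AE test stays because the protocol names it, label it descriptive.
5. Amend protocol 8.2 to match, or record the departure in the SAP.

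With the score-ordered method at 36 per arm (attained size 0.0247), the flag is first raised at 0 vs 4, 1 vs 7 and 2 vs 8 events. Its probability is 99% for 0% vs 25%, 88% for 2% vs 25%, 77% for 50% vs 80% and 95% for 80% vs 100%. With Fisher's test the same four are 92%, 78%, 70% and 75%. The SAP should also state the low sensitivity at rates near 0% vs 10%, so that the absence of a flag is not read as evidence of safety.

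**Cost.** Rewording, a difference and CI column in Table 3, and a protocol amendment or documented departure; no new data. The formal non-inferior-safety statement is lost. Chance flags are at most 2.5% per comparison: for an assumed 10 to 25 organ classes with events and two doses, 10 × 2 × 0.025 = 0.5 to 25 × 2 × 0.025 = 1.25.

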8.1. Additional Exploratory Analyses

A number of additional exploratory analyses are also planned to assess several measures of irritability and other behaviors, and clinical assessments for activity signal, but will not be included as part of the FSR. These additional analyses will include:

- To explore the activity of SRX246 over a period of 12 weeks compared to placebo using measures of irritability and other problem behaviors:
 - Aberrant Behavior Checklist (ABC)
 - Cohen-Mansfield Aggression Inventory (CMAI)
 - Problem Behaviors Assessment – Short Form (PBA-s)
 - Irritability Scale (IS)
 - Unified Huntington Disease Rating Scale (UHDRS)
- To explore the use of the following in irritable study participants with early symptomatic HD who are given SRX246 over a period of 12 weeks compared to placebo:
 - Clinical Global Impression (CGI)
 - HD Quality of Life (HD QoL)
 - Caregiver Burden Questionnaire

9. SAMPLE SIZE JUSTIFICATION

Required sample size was estimated for the primary objective of evaluating the tolerability of SRX246. As previously discussed, this objective will be met by conducting a non-inferiority test of the proportion of completers among the placebo group and each of the treatment groups (separate tests for placebo vs. 120 mg and placebo vs. 160 mg). As described in [section 7](#), the non-inferiority test for the primary objective will be based on exact methods with a computer-intensive ranking procedure to ensure the highest statistical power ([Wang, 2010](#)). It is impractical to use the aforementioned procedure to estimate the required sample size. Therefore, an approximation was used based on the asymptotic test of the difference between two proportions.

Let us again denote the proportion of participants meeting the study definition for tolerability in the placebo group as $\pi_{placebo}$, and the proportion in the 120 mg group as π_{120mg} . The sample size for achieving 80% power for the placebo vs 120 mg groups can be calculated with the following equation,

$$n_{placebo} = \frac{(Z_{.025/2} + Z_{.80/2})^2 \cdot [\pi_{placebo} \cdot (1 - \pi_{placebo}) + \pi_{120mg} \cdot (1 - \pi_{120mg})]}{(\delta - \pi_{placebo} - \pi_{120mg})^2},$$

where δ is the threshold previously discussed, $n_{placebo}$ is the sample size for the placebo group, and the total for the entire study is $N = 3 \cdot n_{placebo}$.

The above equation indicates that a power analysis for this scenario requires estimates for the values of $\pi_{placebo}$, π_{120mg} , and δ . A power analysis was conducted using estimated values of the parameters obtained from previous research. Following the practice of the Huntington Study Group ([HSG, 1998](#); [HSG, 2003](#); [HSG, 2004](#); [HSG/TETRA-HD Investigators, 2009](#)), the margin was set at $\delta = 0.50$ for all analysis. A difference of <50% between groups is considered acceptable because of the paucity of effective treatments for HD ([HSG, 1998](#)). For the remaining parameters, plausible values were based on published literature for relevant randomized clinical trials (RCTs) in HD ([HSG, 1998](#); [HSG, 2003](#); [HSG, 2004](#); [HSG/TETRA-HD Investigators, 2009](#); [Kieburtz et al, 2010](#); [Squitieri et al, 2013](#)). [Table 4](#) below shows completer information for placebo and treatment groups of six HD RCTs employing various drugs (for studies with multiple treatment groups, group with the smallest percentage of completers is shown). Placebo completion rates across the six studies ranged from 82%-97%, and the observed treatment group differences ranged from 0%-18%.

In light of the information in Table 4, sample size was computed for:

- $\pi_{placebo} = 0.80, 0.85, 0.90, 0.95$, and
- $\pi_{placebo} - \pi_{treatment} = 0.01, 0.02, \dots, 0.19, 0.20$.

[figure not shown]
It should be noted that the minimum $\pi_{placebo} = 0.80$ is less than any placebo value in Table 4, and the maximum difference ($\pi_{placebo} - \pi_{120mg}$) of .20 is greater than any observed difference in Table 4. Therefore, these values constitute reasonable bounds for assessing required sample size for this study. The non-inferiority test is single-tailed, and type I error rates of $\alpha = 0.05/2 = 0.025$ and $\alpha = 0.10/2 = 0.05$ were used to allow for two comparisons (each dose level versus placebo), with target power set at 80%.

Table 4. Tolerability Statistics from HD Clinical Trials.

Study	Drug	N	Placebo	Treatment	Difference
HSG (1998)	OPC-14117	64	94%	81%	13%
HSG (2003)	Riluzole	63	91%	87%	4%
HSG (2004)	Minocycline	60	96%	78%	18%
HSG/TETRA-HD (2009)	Tetrabenazine	84	97%	91%	+6%
Kieburtz et al (2010)	Latrepirdine	91	82%	87%	-5%
Squitieri et al (2013)	Pridopidine	353	86%	86%	0%

The results of the power analysis are shown in [Figure 2](#) below. The figure shows the single-arm sample size ($n_{placebo}$) as a function of $\pi_{placebo}$ and the group proportion difference ($\pi_{placebo} - \pi_{120mg}$), paneled by α -level. In the left-hand panel, the upper red line shows that conducting two tests each at $\alpha = 0.025$ and 80% power requires approximately 36 participants per group for the smallest proposed control proportion ($\pi_{placebo} = 0.80$) and the largest proportion difference ($\pi_{placebo} - \pi_{treatment} = 0.20$). Therefore, we proposed a total sample size of $N = 3 \times 36 = 108$. The power analysis suggests that a total sample size of $2 \times 36 = 72$ will be used for each group comparison of completer proportions (120 mg vs placebo, 160 mg vs placebo). The margin used to derive this sample size ($\delta = 0.5$) allows the possibility of a relatively small proportion of completers in the treatment group. For example, if $\pi_{placebo} = 0.90$, H_0 will be rejected if $\pi_{placebo} > 0.04$, meaning there could be a minority of completers.

Figure 2. Sample Size for the Placebo Group as a Function of Effect Size, Placebo Proportion, and Alpha-Level (80% Power)

